5.3 Prior and Concomitant Therapy

With the exception of ordinary over-the-counter moisturizers, and sun protection, no concomitant topical medicines/therapies are permitted for 1 month prior to and during the study period.

5.4 Packaging

The study formulation will be packaged in a ½ pound ointment jar with screw lid. The jars of drug product will be labeled with each subject's name, active contents, expiration, lot number and the following statement: "*EXTERNAL Use Only* *For investigational Use Only*".

5.5 Masking/Blinding of Study

This is an open-label pilot investigation. Masking/blinding procedures are not applicable. Qualitative and quantitative evaluations of response to treatment will be recorded. Updated photographs will be included in participants' records time 0, and week 4.

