6.1 Visit 1 (Week 0/Baseline)

- a) Assess degree of cutaneous involvement by SCORMA Index; Indicate area(s) of the skin to be treated; generate "Global" and "Local" SCORMA values; physical exam/vital signs
- b) Obtain β -HCG. Obtain baseline levels of tryptase, urinary N-MH, LTE4, and 2,3 dinor 11 β PGF2 α if (not obtained during prior 6 months).
- c) Review medical history and current medications
- d) Informed consent
- e) Patient to complete Quality of life questionnaire-SkinDex-16.
- f) Baseline photographs
- g) Review treatment protocol
- h) Dispense study formulation

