6.5 Visit 2-Final visit (Week 2 +/- 1 day)

- a) Reassess cutaneous mastocytosis severity by (Global & Local) SCORMA Indexes; monitor vital signs
- b) Investigator Assessment of Global Improvement
- c) Quality of life assessment:SkinDex-16
- d) Review changes to medical history and current medications
- e) Review contraception (female patients of childbearing potential)
- f) Review adverse events
- g) Review compliance

- h) Repeat photographs
- i) Obtain levels of serum tryptase, urinary N-MH, LTE4, and 2,3 dinor 11β PGF2α
- j) Reconcile study formulation

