7.2.1 Definition of response

Complete response:

Clinically significant SCORMA improvement in all 3 parameters of treated, involved skin: % skin involvement; activity or symptoms &/or

Improvement in all 3 SkinDex-16 domains (Emotions, symptoms, functioning) &/or Resolution of 75% of cutaneous lesions

Near Complete response:

Clinically significant SCORMA improvement in two of 3 parameters of treated, involved skin: % skin involvement; activity or symptoms and/or

Improvement in 2 SkinDex-16 domains (Emotions, symptoms, functioning) &/or Resolution of >50% of cutaneous lesions

Partial Response:

Clinically significant SCORMA improvement in one 3 parameters of treated, involved skin: % skin involvement; activity or symptoms and/or

Improvement in 1 SkinDex-16 domain (Emotions, symptoms, or functioning) &/or Resolution of >25% of cutaneous lesions

No response:

No significant SCORMA improvement in any of 3 parameters of treated, involved skin: % skin involvement; activity or symptoms and/or

Improvement in no SkinDex-16 domain (Emotions, symptoms, functioning) &/or Resolution of no cutaneous lesions.

*Additionally, for primary safety endpoints which will be scored as none, mild, moderate, or severe, the proportion of patients in each category at each follow-up time point will be estimated for each of the different safety endpoints. P-values of 0.05 or lower will be considered as statistically significant.

Handling of missing data

This is a prospective study and therefore we do not anticipate any missing data. In the event of any unexpected missing data, no attempt to impute this missing data will be made; missing data will simply be treated as missing in the statistical analysis.

Multiplicity

Since this is an exploratory pilot study, no adjustment for multiple testing is needed. P-value of 0.05 or lower will be considered as statistically significant.

Primary Hypothesis:

The study seeks to demonstrate the effectiveness and tolerability of a novel topical composition consisting of 3 components (diphenhydramine, aspirin and cromolyn sodium) in a neutral skin moisturizing cream (Vanicream) for the treatment of cutaneous lesions of mastocytosis. This will be determined by the proportion of participants who achieve complete or near-complete response utilizing the SCORMA Index, and SkinDex-16 QOL.

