9.2 Source Documents

Source data is all information, original records of clinical findings, observations, or other activities in a clinical trial necessary for the reconstruction and evaluation of the trial. Source data are contained in source documents. Examples of these original documents, and data records include: hospital records, clinical and office charts, laboratory notes, memoranda, subjects' diaries or evaluation checklists, pharmacy dispensing records, recorded data from automated instruments, copies or transcriptions certified after verification as being accurate and complete, micorfiches, photographic negatives, microfilm or magnetic media, x-rays, subject files, and records kept at the pharmacy, at the laboratories, and at medico-technical departments involved in the clinical trial.

All source documents including clinical findings, observations or other activities will be stored in a REDCap database that will be designated by the Statistician. Access to the REDCap database will be limited to the Principal Investigator, Investigators, and Statistician.

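### Section 5.5 sets masking aside, yet the scheduled Week 0 and Week 2 photographs could be read masked to visit order to check the lesion-resolution limb of response

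*Combined protocol and SAP*

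**What the plan says.** Section 5.5 states: "Masking/blinding procedures are not applicable. Qualitative and quantitative evaluations of response to treatment will be recorded". Its next sentence gives photographs their only described role: "Updated photographs will be included in participants' records time 0, and week 4".

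The visit lists schedule photographs twice: "Baseline photographs" at Visit 1 (6.1, item f) and "Repeat photographs" at the Week 2 visit (6.5, item h). The schedule in 6.6 marks both. Neither the endpoints (3.2), the response definition (7.2.1), the baseline-to-follow-up analysis nor the attached response forms mention them.

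Section 7.2.1 builds each response category from three limbs joined by and/or: SCORMA parameters, SkinDex-16 domains and percent lesion resolution. The lesion limb for near-complete response is "Resolution of >50% of cutaneous lesions"; for complete response the figure is 75%. No rater or method is given for this percentage. The response forms have a column for it, also without a named rater. Section 6.6 lists an investigator assessment of clinical response at both visits, and 6.5 adds an investigator rating of global improvement. The design (3.1) is nonrandomized and open-label, with no control group.

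**The concern.** Open treatment does not make masking irrelevant to assessment. In a before-after study, what can be hidden is which visit is being judged, and photographs allow that. Percent lesion resolution is a visual judgement with no stated method, and it can decide the primary outcome for a patient. A rater who knows that the patient has just finished treatment may lean towards improvement, and would lean the same way in every patient. With no concurrent control, that lean looks the same as a treatment effect. Section 7.1 says the data are meant to give a preliminary estimate of efficacy and to inform a larger study, so the bias would carry forward.

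**Working it through.** The plan gives no effect size, SD or power figure, so there is nothing of its own to reproduce. The check has three parts.

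**1. Which lesion cut-offs can move the primary proportion.** The primary measure is the share of patients with complete or near-complete response (3.2 and the Primary Hypothesis), with 10 patients (7.1).

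| Lesion cut-off in 7.2.1 | Change of category by the lesion limb | Effect on the primary proportion |
|---|---|---|
| >25% | none to partial | none |
| >50% | partial to near-complete | 1/10 = 10 percentage points, if the patient does not already qualify through SCORMA or SkinDex-16 |
| 75% | near-complete to complete | none |

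Two patients misjudged at the >50% cut-off would move the result by 2/10 = 20 points.

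**2. What unmasked scoring can do more generally (illustration).** SCORMA is A/5 + 5B + 2C/5 (3.2). One grade on one of the four intensity items is worth 5 × 1 = 5 points. The plan tests change with a paired Wilcoxon signed-rank test at 0.05; I take it as two-sided.

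- *Without assuming an SD.* If the rater lowers one item by one grade in k patients and the rest are unchanged, with zeros dropped, the exact p is 2 × 0.5^k. For k = 5 this is 0.0625, for k = 6 it is 0.031, and for k = 10 it is 0.002. Six of 10 patients are enough.
- *With an assumed SD.* The setting is no true change, a 5-point average drift, normal changes, n = 10 and 100,000 simulated trials, rejecting when the smaller rank sum is 8 or less (exact level 0.0488). The table shows how often a significant improvement appears.

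| SD of change (assumed) | No drift | 5-point drift |
|---|---|---|
| 5 | 2.4% | 78.4% |
| 10 | 2.5% | 28.3% |
| 15 | 2.4% | 15.1% |

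The drift and the SDs are assumptions; the documents give neither.

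**3. How far photographs could reach.** Take C as the sum of five 0–10 scales and the treated area as 18% of the skin, the upper limit in 3.2. The local SCORMA maximum is then 18/5 + 5 × 12 + 2 × 50/5 = 3.6 + 60 + 20 = 83.6. Extent plus pigmentation/erythema, the parts a photograph shows well, come to at most 3.6 + 15 = 18.6 points, and 18.6/83.6 = 22%. Darier's sign needs skin contact, elevation shows poorly, and symptoms are reported by the patient. A photograph reading therefore suits the lesion limb and cannot stand in for SCORMA.

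**The case against.** The strongest reply is that open-label proof of concept is a declared choice. Nothing in 5.5 contradicts the rest of the plan on masking, and a masked reading is an optional supplement. That stands: this is a correctable weakness, not an error.

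Several stronger readings are tempting and not supported.

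- *The photographs are never used and every visual outcome is scored only live.* This would rest on silence. Section 7.2.1 names no method for percent resolution, and the photograph sentence in 5.5 directly follows the one on recording response, so some informal use is possible. What can be said is that no rating or analysis use is specified.
- *The baseline score is in view when Week 2 is scored.* The two-row response tables are summaries that need both values, while the SCORMA form has its own visit-date field, which suggests one form per visit.
- *Any crossed cut-off moves the result by 10 points.* Only the >50% cut-off can, and only for a patient not already qualifying by another limb.
- *A masked photograph reading would remove the simulated inflation.* It would not. Those figures concern the SCORMA signed-rank test, which would still use live scores.

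It is also fair to say that masking may be imperfect. The plan does not standardise photograph conditions or say which skin is photographed, and a study investigator has access to the records: "Access to the REDCap database will be limited to the Principal Investigator, Investigators, and Statistician".

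**Conclusion.** The point holds as a low-cost improvement. Percent lesion resolution has no named masked rater, can confer primary response by itself under the and/or wording, and is judged in a study with no control arm. Photographs that would allow an order-masked check are already scheduled. The size is 10 percentage points on the primary proportion for each patient misjudged across the >50% cut-off who would not otherwise qualify. This rests on reading the and/or wording so that any one limb suffices; the Primary Hypothesis names only SCORMA and SkinDex-16, but 7.2.1 includes the lesion limb.

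The rise from 2.5% to about 28% (SD 10; 15% at SD 15, 78% at SD 5) shows the general risk of unmasked scoring under an assumed 5-point drift. It does not measure what the fix would gain.

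**What to change.** **Section 5.5.** State that treatment is open but that photographs of the treated area are read masked to visit order. Reconcile the week 4 photograph date there with the Week 2 photographs in 6.5 and 6.6.

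**Reading.** After the last patient's final visit, the statistician strips dates and presents each patient's two image sets side by side in random order (10 × 2 = 20 sets). The comparison must be paired, because resolution cannot be judged from one undated set. An investigator already on the study, where possible not the one who scored that patient, records which set shows less disease and the percent difference in lesions. The statistician then decodes. If the Week 0 set was judged to show less disease, the lesion limb counts as no resolution.

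**Section 7.2.1.** Report the masked lesion-resolution category, and the primary proportion recomputed with it, beside the live result as a sensitivity analysis. State how many patients lack a usable pair of image sets.

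**Cost and limits.** The change needs protocol wording and a few hours of existing staff time, with no extra staff, visit or patient procedure. Only the lesion limb is protected. Darier's sign, elevation, symptoms, SkinDex-16 and the SCORMA signed-rank test stay unmasked. Taking both sets under similar conditions, and keeping the reader out of the database while reading, would make the masking less porous.

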5.6 Receiving, Storage, Dispensing and Return

5.6.1Receipt of Drug Supplies: The study formulation will be compounded by the Mayo Clinic Research Pharmacy in Minnesota for each subject.

- 5.6.2 Storage: The study formulation will be stored at room temperature 68° to 77° F (20°-25°C), with excursions permitted between 59° to 86°F (15°-30°C), by the Mayo Clinic Research Pharmacy in Minnesota. There are no special handling requirements.
- **5.6.3 Dispensing of Study Drug:** Finalreconciliation by weight measurement and/or number of returned empty jars will be performed by the Principal Investigator or study team member to document study formulation dispensed and returned. This reconciliation will be logged on the Case Report Form, and signed and dated by the Principal Investigator and/or investigators.
- **5.6.4 Return or Destruction of Study Drug:** At the completion of the study, there will be a final reconciliation of the study formulation dispensed, returned and remaining. This reconciliation will be logged on the Case Report Form, signed and dated. Any discrepancies noted will be documented and investigated. Drug destroyed on site will be documented. Participants will be required to return any unused study drug at the end of the study period.

6.1 Visit 1 (Week 0/Baseline)

- a) Assess degree of cutaneous involvement by SCORMA Index; Indicate area(s) of the skin to be treated; generate "Global" and "Local" SCORMA values; physical exam/vital signs
- b) Obtain β -HCG. Obtain baseline levels of tryptase, urinary N-MH, LTE4, and 2,3 dinor 11 β PGF2 α if (not obtained during prior 6 months).
- c) Review medical history and current medications
- d) Informed consent
- e) Patient to complete Quality of life questionnaire-SkinDex-16.
- f) Baseline photographs
- g) Review treatment protocol
- h) Dispense study formulation

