3.1 General design

This is a phase II nonrandomized, open-label pilot study of the effectiveness and tolerability of a novel composition comprised of daily application of trolamine salicylate 10%, sodium cromolyn 5%, and diphenhydramine 1% in vanicream on skin producing cutaneous symptoms of mastocytosis. Subjects will be screened by the Department of Allergic Diseases at the Mayo Clinic in Rochester MN and interested qualified subjects will be consented and offered participation. The study is designed to establish

feasibility/proof of concept and will not include randomization or crossover components. Please see Section 6: Study procedures for a detailed description.

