3.3 Secondary Study Endpoints

These will include mast cell mediator levels; serum tryptase, urinary leukotriene (LT) E4, n-methyl histamine (N-MH), and 2,3 dinor 11β prostaglandin(PG) F2α levels [Mayo Medical Labs].

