4.1 Inclusion criteria

Informed subject consent will be obtained from those patients with the following inclusion criteria:

- Biopsy proven cutaneous mastocytosis with or without evidence of systemic disease
- Male and female patients 18 to 80 years of age
- No UVB treatment of the skin for 6 months prior to study entry
- No use of topical or systemic corticosteroids for 1 month prior to study entry
- Good general health as confirmed by medical history
- Female patients of child-bearing potential with negative urine pregnancy test who agree to use effective methods of birth control or remain abstinent during treatment. Participants must use birth control for the entire study and for at least 1 week after the last application of the study formulation. Acceptable methods of birth control include ongoing hormonal contraception methods, (such as birth control pills, patches, injections, vaginal ring, or implants), barrier methods (such as a condom (for men) or diaphragm used with a spermicide), intrauterine devices, tubal ligation, or abstinence.
- Patients who are willing and capable of cooperating to the extent and degree required by the protocol; and
- Patients who read and sign an approved informed consent for this study

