6.6 Protocol Schedule of Events

	Week 0	Week
Study Activity	Screening &	2
	Baseline	
Visit Number	1	2
Allowable visit window in days		+/- 1
Review Eligibility	X	
Informed Consent	X	
Medical History	X	X
Dispense/Reconcile Medications	X	X
Review Changes to Medical History and Medications		X
Quality of Life Scale:SkinDex-16	X	X
SCORMA Index	X	X
Physical Exam	X	
Serum Tryptase, & urinary Mast cell mediators	X	X
Investigator Assessment of clinical response: initial and	X	X
subsequent; vital signs		
Photography	X	X
Adverse Event (Physician)		X
Adverse Event (Participant)		X
Review Dosing Compliance		X
Review Contraception	X	X
β-HCG ^a	X	
·		
a: Urine pregnancy test (women of childbearing potential)		

7 Statistical Plan

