7.1 Sample Size determination

Due to the pilot nature of the study, no formal statistical power/sample size calculations are necessary. The sample size of 10 patients will be sufficient for this pilot study to obtain a preliminary estimate of treatment efficacy and to generate data that will be useful in the design of a larger study.

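### Section 6.1(b) lets a mediator result up to 6 months old stand in for the Visit 1 baseline, although the schedule in 6.6 takes the sample at Week 0 for everyone

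*Combined protocol and SAP*

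**What the plan says.** Section 3.3 gives the secondary endpoints ("These will include mast cell mediator levels") and names four: serum tryptase, urinary LTE4, N-MH and 2,3 dinor 11β PGF2α.

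Three places in Section 6 deal with when they are measured:

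- **6.1(b), Visit 1:** baseline levels of all four are obtained "if (not obtained during prior 6 months". The bracket is awkwardly placed, but the natural reading is that an earlier result replaces the Visit 1 sample.
- **6.5(i), Visit 2:** "Obtain levels of serum tryptase, urinary N-MH, LTE4" and the fourth mediator, with no condition.
- **6.6, schedule:** the row "Serum Tryptase, & urinary Mast cell mediators" is marked at Week 0 and at Week 2. The table's only footnote concerns the pregnancy test.

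Section 3.1 says that the study "will not include randomization or crossover components", so there is no concurrent comparator. Section 7.1 says that one purpose of the 10 patients is "to generate data that will be useful in the design of a larger study". Section 7.2 gives general descriptive summaries for continuous variables. The paired Wilcoxon test under 7.2.1 is named for SCORMA and SkinDex-16 only.

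**The concern.** Two sections give different instructions for the same sample. Staff who follow 6.1(b) will skip a draw that 6.6 schedules, and a pre-treatment sample that was not taken cannot be recovered once the cream has been applied.

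In a single-arm study the baseline carries the whole comparison. If it was taken months earlier, the difference between it and the Week 2 level combines whatever happened before the study with whatever happened on treatment, and the data cannot separate the two. If some patients have a Visit 1 baseline and others an older one, their changes span different intervals and may not be comparable. A standard deviation of change pooled over intervals of about 2 to 28 weeks would be hard to use in planning a larger study.

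The washout windows add a second route. Section 4.1 requires "No use of topical or systemic corticosteroids for 1 month prior to study entry", and 4.2 and 5.3 set 1-month limits for listed systemic agents and for topical therapies. A result more than 1 month old predates those windows, so it may have been obtained on a treatment that was then stopped to qualify for entry.

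**Working it through.** The plan states no figure for mediator change, so there is nothing of its own to reproduce. The check is a comparison of the text followed by simple arithmetic on the interval between samples.

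**1. Do the sections conflict?** 6.1(b) is conditional. The mediator row of 6.6 is unconditional, and 6.5(i) is unconditional at Week 2. No section says which of 6.1(b) and 6.6 governs, calls for the date of a reused result, or plans a sensitivity analysis for it.

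**2. Interval between baseline and Week 2.** Inputs:

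- Visit 2 is at day 14, plus or minus 1 day (6.5 and 6.6).
- The oldest reusable result is 6 months old (6.1(b)), taken as 183 days.
- Ages of 1 month (30 days) and 3 months (91 days) are illustrations and are not in the documents.

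Formulas, for a result of age *a* days at Visit 1: interval = *a* + 14; multiple of the planned interval = (*a* + 14)/14; treatment share = 14/(*a* + 14).

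| Baseline | Interval (days) | Multiple of 14 days | Treatment share |
|---|---|---|---|
| Visit 1 sample | 14 (13 to 15) | 1 | 100% |
| 1 month old | 30 + 14 = 44 | 3.1 | 14/44 = 31.8% |
| 3 months old | 91 + 14 = 105 | 7.5 | 14/105 = 13.3% |
| 6 months old (limit) | 183 + 14 = 197 | 14.1 | 14/197 = 7.1% |

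With the visit window, the interval at the limit runs from 183 + 13 = 196 to 183 + 15 = 198 days (28.0 to 28.3 weeks), and the treatment share from 13/196 = 6.6% to 15/198 = 7.6%. About 93% of the interval (183/197) then lies before treatment.

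**3. Look-back against washouts.** The look-back is 6 months. The windows for corticosteroids (4.1), listed systemic agents (4.2) and topical therapies (5.3) are 1 month. Results between 1 and 6 months old therefore fall in a period when those treatments were not barred. UVB is different: 4.1 asks for "No UVB treatment of the skin for 6 months prior to study entry", which matches the look-back, so the argument does not extend to UVB.

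**4. Does Section 7 settle which baseline counts?** No. It names no analysis of mediator change, so it does not say whether a reused result qualifies as baseline.

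**5. Are other endpoints affected?** No. SCORMA and SkinDex-16 are recorded at both visits under 6.1, 6.5 and 6.6.

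**The case against.** The strongest reply is that the affected analysis is not one the plan states. Section 3.3 lists levels, not changes, and the only paired test is for the primary measures. That is true. But 6.1(b) itself calls the value a baseline and 6.5(i) repeats the test after treatment, so a before-after reading is the evident purpose. The absence of a mediator analysis also means that nothing elsewhere limits the damage.

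A second reply is that elapsed time is not bias. If a mediator is stable within a patient, a value several months old does no harm, and one a few days old differs little from a Visit 1 sample. This stands. The documents give no within-patient variation or drift, so the multiples and percentages above describe the comparison and do not measure an error in it. The washout route likewise needs a patient to have used a barred agent, stopped it after the old sample, and had mediator levels altered by it. That is possible and not shown.

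Third, a mark in a schedule table can be read as shorthand for the conditional visit text. On that reading a compulsory Visit 1 sample is an added procedure for patients who already have a result. The cost is still bounded by 10 patients.

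Finally, this is a small pilot and the endpoint is secondary, so reusing recent clinical results is an understandable economy. That limits how much weight the point carries. It does not remove the conflict between the sections.

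**Conclusion.** The concern holds. The rule in 6.1(b) conflicts with 6.6 and, if followed, gives a weaker comparison than the schedule would: up to about 28 weeks between samples in place of 2, with about 7% of that time on treatment at the limit.

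This rests on reading the condition as covering all four mediators, on 6 months being 183 days, and on the 2-week visit schedule in 6.5 and 6.6. Calendar spans of 181 to 184 days would widen the range at the limit to 194 to 199 days (181 + 13 to 184 + 15), which changes nothing of substance. The Study Summary and 5.5 also mention four weeks or week 4. Those passages need reconciling separately.

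The number of patients with a reusable result, and the direction and size of any bias, cannot be determined from the documents; if no patient has an earlier result, the effect is nil. A Visit 1 sample removes the long gap and the pre-washout exposure, but not natural variation or the lack of a control group. The point should be corrected because it bears on all four secondary endpoints and is easily put right. It does not threaten the primary results.

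**What to change.** 1. In 6.1(b), delete the condition "if (not obtained during prior 6 months" with its closing bracket, so that all four mediators are sampled at Visit 1, before the first application, for every patient. This makes 6.1(b) agree with 6.6.
2. In Section 7, define mediator change as the Visit 2 level minus the Visit 1 level, summarised with the descriptive statistics already listed in 7.2.
3. If an older value has to be used for a patient, record its date on the case report form and report that patient separately from those with a Visit 1 baseline.

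The cost is wording plus at most 10 sets of blood and urine tests, which 6.6 already shows. The documents give no price for them. Separate reporting of older baselines discards no data.
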